The training protocol will be delivered by the Nintendo® Wii balance board and consists of repetitions of several games selected from the “Wii Fit Plus” package ([http:// www.wiifit.com/training/balance-games.html](http://www.wiifit.com/training/balance-games.html)). Each game starts at basic level, and when a certain score is reached, patients is automatically transferred to a more advanced level. Patients will be encouraged to play the next game if they have a level progress; otherwise, 10 minutes will be allocated for each game. During the first 4 weeks of training, patients will be allowed to play only “Zazen” (sitting position), “Table Tilt” and “Ski Slalom”; thereafter they will add the remaining games “Penguin Slide”, “Tightrope Walk”, “Balance Bubble” and “Soccer Heading” [9].

Adaptive COGNI-TRAcK (comparator intervention)

The training protocol will be delivered by a dedicated app for mobile devices (mobile phone or tablet). The app implements three different types of exercises (each one executed for about 10 min a session), consisting in a visuo-spatial working memory task, an “operation” N-back task and a “dual” N-back task. The adaptive training is structured so that the exercises difficulty level will increase by one step every time the user will perform a correct exercise. On the other hand, the difficulty level will decrease by one step if the exercise is incorrect for three times in a row [24].

Sham COGNI-TRAcK (placebo-analogue intervention)

The training protocol will be delivered by a dedicated app for mobile devices (mobile phone or tablet) as previously described for adaptive COGNI-TRAcK [24]. However, the non-adaptive training (placebo-analogue intervention) consists in an algorithm implementing two low difficulty levels alternating every day regardless of the user’s performance.

Concomitant medications

Patients are encouraged to continue his/her disease-modifying treatment (DMT) and symptomatic treatments without change in dosage or administration frequency throughout the entire study period. Any change in pharmacological treatment, including DMT, during the study must be recorded. As per eligibility criteria, patients who change any medication over the previous 3 months should be not enrolled.

Forbidden treatments and interventions

No pharmacological treatment is strictly forbidden; however, patients are encouraged to not start pharmacological treatments that can potentially impact on cognition, namely antidepressants, dalfampridine, nabiximols, modafinil, amantadine, dopamine-agonists.

Steroid administration due to MS relapse or any symptomatic drug initiation due to any MS-related symptom should be considered as an AE.

Patients are encouraged to not start any other type of physiotherapy or rehabilitation during the study period, but they are encouraged to continue his/her physiotherapy or rehabilitation program if started at least 3 months before the study enrolment.

STATISTICAL PLAN

Sample size estimation

Overall, we will randomize **126 patients** (considering even a 20% drop-out rate), based on two previously published studies that have found:

- (i) a significant effect of an home-based cognitive training using the [name]® Brain Training that promoted an about 8-point mean increase at SDMT score (with respect to wait-list group) [53];
- (ii) a significant effect of adaptive COGNI-TRAcK that promoted an about 8-point mean increase at SDMT score (with respect to a sham intervention) [24];
- (iii) a 50%-difference in proportions of responders (10/14 versus 3/14 in adaptive COGNI-TRAcK group and sham COGNI-TRAcK group, respectively) [24], according to a responder definition of SDMT change approximating 4 points or 10% in magnitude [28].

For the non-inferiority comparison, the null hypothesis is that the intervention with exergames is inferior to adaptive COGNI-TRAcK, while the alternative hypothesis is that the intervention with exergames is non-inferior to adaptive COGNI-TRAcK by a pre-defined amount of SMDT score.

If there is truly no difference between exergames and adaptive COGNI-TRAcK, then 35 patients per arm are required to ensure, with a statistical power of approximately 85%, that the lower limit of a one-sided 95% confidence interval (or equivalently a 90% two-sided confidence interval) will be above the predefined non-inferiority margin of 8-point change in SDMT.

For the superiority comparison, the null hypothesis is that the intervention with adaptive COGNI-TRAcK is not superior to sham COGNI-TRAcK, while the alternative hypothesis is that the intervention with adaptive COGNI-TRAcK is superior to sham COGNI-TRAcK in increasing the proportion of responders as afore defined. Enrolling 35 patient per arm will ensure a more than 95% power in detecting a statistical significance between-group difference of 50% at two-sided alpha level of 5%.

Statistical analysis

All analysis will be based on the intention-to-treat principle using the fully analysis dataset including all randomized patients. Missing data will be handled by multiple imputation method, with the assumption that some data will be missed completely at random.

Efficacy analyses: efficacy data will be analyzed by parametric and/or non-parametric Repeated Measures Analyses of the Variance (RM-ANOVAs) with effect size estimation. In each analysis, we will consider as dependent variable all measures or score derived from study assessments; the three study visits (Baseline, Week 8 and Week 16) as within-subject factors; and intervention arms (exergames, adaptive COGNI-TRAcK and sham COGNI-TRAcK) as between-subject factors. Effect sizes will be estimated as Cohen's F-squared, rated as small, medium, and large for values of 0.02, 0.15, and 0.35, respectively [54].

Safety data regarding time to first accidental falls will be analyzed as time-to-event data by Kaplan-Meier curves and Log-Rank test with a factor for intervention arms.

Safety analyses: data regarding the occurrence of adverse events during the intervention period and the follow-up period will be analyzed by the Chi-squared test comparing the independent distribution of events according to intervention arms.

Predictors of outcomes: logistic regression analyses will test if the achievement of a clinically relevant change in the pre-planned endpoints is predicted by scores derived from CRIQ, HLAQ and TCI, after controlling for a set of baseline covariates including sex, age, disease duration, EDSS score, performance on the explored task. For those endpoints lacking of a definition of clinically relevant change, we will adopt Analyses of Covariance (ANCOVAs) with immediate post-training score as dependent variables, intervention arm as fixed factor and a set of baseline covariates including sex, age, disease duration, EDSS score, baseline performance on the explored task, as well as scores derived from CRIQ, HLAQ and TCI as covariates of interest.

Pre-planned statistical significance level

Exergames and adaptive COGNI-TRAcK will be compared with sham COGNI-TRAsK as placebo-analogue arm. Therefore, all analysis will be corrected with Bonferroni adjustment for multiple comparisons of two-sided tests, giving a two-sided significant p-value of 0.025.

Interim analysis

An interim analysis will be conducted when at least 50% of the estimated sample size will complete the 8-week intervention period.

STUDY GOVERNANCE AND OVERSIGHT

Steering committee

The steering committee shall comprise the Principal Investigator (PI) and all the co-investigators reported in this study protocol.

The steering committee will be responsible for the overall design, interpretation, supervising and reporting (presenting at national and international congresses and publishing in peer-reviewed journals). Members of steering committee will be also responsible for providing clinical guidance on study implementation and conduct in their respective sites.

Data Monitoring

An independent Data Monitoring Committee (DCM) will be appointed to review the overall conduct of the study, with particular attention to eligibility criteria, randomization, and collection of efficacy and safety data. The DCM will have access to the individual treatment codes while the study is ongoing; therefore, if DMC expresses safety concerns, appropriate information will be sent to the PI, regulatory authorities and study funder Associazione Italiana Sclerosi Multipla (AISM).

The DCM is also responsible for ensuring the maintenance of blinding and integrity of the study.

ETHICAL AND REGULATORY REQUIREMENTS

Ethical conduct of the study

This study will be performed in accordance with specific national laws and the ethics standards laid down in the 1964 Declaration of Helsinki and its later amendments.

Ethical principles adopted in this study are consistent with International Conference on Harmonization/GCP applicable to biomedical research on human subjects [46] and with the FISM ethical code (provided as appendix).

There is no incentive for patients who participate in the study.

In no way this study will interfere with the standard care offered to patients with MS in each involved sites, in particular regarding scheduled or unscheduled outpatient activities, including clinical, laboratory and MRI follow-up and management of DMT or any symptomatic treatment.

Informed consent and patient data protection

The Institutional Ethic Committee (IEC) of the PI site should approve the final version of the study protocol, informed consent form and any other written information and/or materials provided to patients recruited in this study. The PI is responsible for the distribution of these documents to the lead IEC and, once obtained the approval, to the other applicable IEC and to the staff of all study sites.

The PI and co-investigators at each site will ensure that:

- each patient is given full and adequate oral and written information about the nature, purpose possible risk and benefit of the study;
- each patient is notified that they are free to discontinue from the study at any time, without prejudice for further treatment or care;
- each patient is given the opportunity to ask questions and allowed time to consider the information provided;
- the original signed informed consent form is stored in the study file at site;
- a copy of the signed consent form is given to the patient.

The informed consent form will incorporate wording that complies with relevant data protection and privacy legislation.

Insurance

Even if the present research does not encompass any pharmacological or surgical intervention, and even if neither exergames nor COGNI-TRAcK are associated with relevant AE or side effects (see also the paragraph “Risk:benefit ratio and ethical consideration”), we will stipulate an insurance policy to grant specific cover in connection with the reimbursement of damages caused to the subjects by the study activities throughout the entire duration thereof, thus covering any civil liability of investigator and sponsor of the clinical trial, without excluding any damage which may be unintentionally caused by accident and/or be attributed to negligence, imprudence or inexperience.

PI and co-investigators will inform the participants to the study protocol, even through the informed consent, that the insurance policy covering damages caused by civil liability (as third party liability) in the study will not cover any amount exceeding its limit of liability and that such policy exclusively applies to damages for which a claim was submitted within and not later than the period provided in the policy. This restriction shall not in any event impair the right of the damaged party to seek reimbursement of damages from the person liable therefor. Insurance shall cover death, all permanent and/or temporary impairment of health conditions, relevant financial consequential losses which are the direct consequence of the study and which can be traced to the liability of all people operating for the performance of the study.

Audits and inspections

Authorized representative of regulatory authority, IEC or AISM/FISM may perform audit or inspections at any site, including source data verification. The reference Institution/Hosting Organization shall ensure due collaboration to allow such meetings and visits to take place. Participation in the progress and final report meetings organized by AISM/FISM is required per each annual period of the duration of the project and for the year following the closure of the project.

REFERENCES

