We estimated a pre-defined 8-point non-inferiority margin, based on a significant effect of the COGNI-TRAcK in inducing an about 8-point mean increase at SDMT score (with respect to a sham intervention). Accordingly, 35 subjects per arm are required to ensure, with an approximately 85%-power level, that the lower limit of a one-side 95% confidence interval will be above the pre-defined non-inferiority margin. Therefore, considering also a drop-out rate of 25%, a total of 132 subjects should be enrolled.

Statistical methods

All analysis will be based on the intention-to-treat principle using the fully analysis dataset including all randomized patients. Missing data will be handled by multiple imputation method. Continuous data will be analyzed by parametric and non-parametric RM-ANOVAs with effect size estimation. The time-to-event data will be analyzed by Kaplan-Meier curves and Log-Rank test with a factor for treatment group.

An interim analysis will be conducted when at least 50% of the estimated sample size will complete the 8-week intervention period.

Study objectives

Primary objective	Primary endpoint
To demonstrate not inferior efficacy of exergames over COGNI-TRAcK and superior efficacy of both interventions over sham in improving sustained attention and information processing speed	Change at the SDMT from baseline to Week 8
Secondary objectives	Secondary endpoints
To demonstrate not inferior efficacy of exergames over COGNI-TRAcK and superior efficacy of both interventions over sham in improving cognitive functions	Change at the BICAMS and SCWT from baseline to Week 8
Additional objectives	Additional endpoints
To demonstrate not inferior efficacy of exergames over COGNI-TRAcK and superior efficacy of both interventions over sham in reducing the impact of MS on: - cognitive-motor interference - activities of daily living - fatigue - work productivity	Change of dual-task cost of walking and balance as estimated by the 2MWT and static posturography in dual-task vs. single-task condition from baseline to Week 8 Change at the MSIS-29 from baseline to Week 8 Change at the MFIS from baseline to Week 8 Change at the WPAI:MS from baseline to Week 8
Exploratory objectives	Exploratory endpoints
To demonstrate not inferior efficacy of exergames over COGNI-TRAcK and superior efficacy of both interventions over sham on: - physical activity - adherence	Physical activity measured by wearable actigraph Percentage of training completed at home

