
Rationale for study design and duration

This is a multi-centre, 16-week (8-week intervention followed by 8-week follow-up), randomized, single-blind, parallel-arm study comparing three different types of home-based training:

- (1) active video games of balance delivered by the Wii balance board, from here onwards called **‘exergames’** (intervention of interest);
- (2) Cognitive Training Kit (COGNI-TRAcK) with increasing difficulty levels, from here onwards called **‘adaptive COGNI-TRAcK’** (comparator intervention);
- (3) COGNI-TRAcK at constant difficulty level, from here onwards called **‘sham COGNI-TRAcK’** (placebo-analogue intervention) [24].

This study design will allow us to test the hypotheses that (i) exergames and adaptive COGNI-TRAcK are more effective than sham adaptive COGNI-TRAcK; (ii) exergames are not inferior to adaptive COGNI-TRAcK.

The choice of an 8-week study duration was based on previously published papers on cognitive training delivered by COGNI-TRAcK. In this study, 8 weeks of adaptive COGNI-TRAcK training were sufficient to determine a significant improvement in the SDMT score when compared with sham COGNI-TRAcK, yielding to a post-training between-arm difference of 8 points ($p < 0.001$) [24].

The 8-week post-training follow-up period will allow us to investigate the retention of training effect, which is an underinvestigated topic in MS rehabilitation setting. Literature data provide conflicting results (no retention for exergames, 6-month retention for cognitive rehabilitation) [9],[24].

Rationale for interventions

Exergames (the portmanteaux for “exercise” and “video games”) represent a form of whole-body physical exercise performed through active video games. Playing exergames involves not only the hand-eye coordination, but also whole body physical exertion, with the aim of improving fitness and promoting an active lifestyle [8]. Unlike the fully immersive VR (that simulates a lifelike multisensorial experience in a 3-dimensional artificial environment), the non-immersive VR involves the use of smaller-scale, 2-dimensional environment (e.g. home TV, computer display, etc) and interface devices, such as balance board, motion controllers or cameras equipped with depth sensors that can also provide haptic or kinesthetic communication reproducing tactile sensations by applying forces, vibrations or motions [7].

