Patients with MS, regardless of disease course, who fulfil all inclusion criteria and none of the exclusion criteria, will be randomized in a 1:1:1 ratio to exergames or adaptive COGNI-TRAcK or sham COGNI-TRAcK. This study includes two periods (training period and follow-up period) and three visits (see the **FIGURE** below):

- on Week 0, at study enrolment/randomization (baseline visit);
- on Week 8 (+/- 5 days), i.e. after the end of the 8-week training period (Week 8 visit);
- on Week 16 (+/-5 days), i.e. at study termination after the 8-week post-training follow-up period (Week 16 visit).

Eligibility criteria

For inclusion:

- (i) age between 18 and 55 years (inclusive);
- (ii) cognitive impairment, defined as failure in the SDMT, defined as a corrected score less than 38, i.e. below the 5th percentile of normative value [31];
- (iii) Expanded Disability Status Scale (EDSS) score between 2.0 and 5.5 [32];
- (iv) ability to stand upright for at least 180 seconds without any support;
- (v) ability to understand and comply with study requirements;
- (vi) ability to provide a valid informed consent before any study procedure.

For exclusion:

- (i) relapse in the previous 6 months;
- (ii) initiation of disease-modifying or symptomatic treatments or physiotherapy programme in the 3 months prior to study entry;
- (iii) any medication/physiotherapy changes occurring over the previous 3 months;
- (iv) significant visual impairment, defined as a Visual System scoring more than 2 at the Kurtzke Functional Systems Score [32];
- (v) clinically relevant depression, defined as Beck Depression Inventory-II (BDI-II) score equal or more than 14 [33];
- (vi) overt dementia, defined as an adjusted Mini Mental State Examination (MMSE) score equal or less than 24 [34];
- (vii) history of epilepsy or seizures;
- (viii) any medical condition, including musculoskeletal disorders that can interfere with the study conduction.

Randomization procedure

Randomization codes will be computer-generated in blocks of six to ensure an approximate 1:1:1 balance between the three arms. Randomization codes will be assigned at baseline visit sequentially within each center as patients become eligible for randomization by an independent organization not involved in study conduction. Once a block is exhausted, the next available block will be allocated to a center upon the next randomization.

Blinding

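### Patients in an ongoing cognitive rehabilitation programme can enrol and are encouraged to continue it, which can dilute the contrasts with sham and ease the non-inferiority test

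*Protocol*

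**What the plan says.** Two exclusion criteria in the Protocol, Eligibility criteria, deal with background therapy. One bars "initiation of disease-modifying or symptomatic treatments or physiotherapy programme in the 3 months prior to study entry"; the other bars "any medication/physiotherapy changes occurring over the previous 3 months". No criterion mentions cognitive rehabilitation or cognitive training, whether ongoing or completed.

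The section Forbidden treatments and interventions covers rehabilitation during the trial. New programmes are discouraged but not forbidden: "Patients are encouraged to not start any other type of physiotherapy or rehabilitation during the study period". For existing ones, "they are encouraged to continue his/her physiotherapy or rehabilitation program if started at least 3 months before the study enrolment".

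Three other statements bear on this:
- The primary endpoint is "Change at the SDMT from baseline to Week 8" (synopsis, Study objectives), and entry requires SDMT failure, "defined as a corrected score less than 38, i.e. below the 5th percentile of normative value".
- Sample size estimation rests in part on "a significant effect of adaptive COGNI-TRAcK that promoted an about 8-point mean increase at SDMT score (with respect to a sham intervention", and sets the non-inferiority margin at the same 8 points.
- Rationale for study design and duration describes the literature on retention as conflicting and summarises it as "no retention for exergames, 6-month retention for cognitive rehabilitation".

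**The concern.** The sham arm is meant to show what happens to the SDMT without effective cognitive training. As written, a sham patient whose cognitive programme began four months before enrolment meets every listed criterion on background therapy and is encouraged to carry on with it. That patient receives active training in the tested domain throughout the measurement period. The same applies in the other two arms, where a patient already in training may have less to gain from the study intervention.

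If background training uses up part of the achievable gain, all between-arm differences shrink. For the two superiority claims this costs power. For exergames against adaptive COGNI-TRAcK the bias is anti-conservative, because a smaller difference looks more like non-inferiority. The margin leaves no reserve: it equals the full cited effect over sham, so exergames with no effect at all over sham would sit exactly on the margin, and any attenuation moves them inside it.

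**Working it through.** **Reading the sections together**

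| Patient at enrolment | Eligibility criteria | Continuation sentence |
|---|---|---|
| Cognitive programme ongoing, begun at least 3 months ago | Not excluded | Applies: continuation encouraged |
| Cognitive programme begun within 3 months | Not named; excluded only if it counts as a symptomatic treatment | Does not apply |
| Cognitive programme recently completed | Not excluded | Does not apply |

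The first row is the main problem. The Protocol uses the word rehabilitation for cognitive as well as motor work (Background and rationale; Rationale for study design and duration), so the sentence cannot safely be read as motor only.

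**Reproducing the plan's figures**

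*Superiority.* Inputs from Sample size estimation: responders 10/14 = 0.714 and 3/14 = 0.214, 35 per arm, two-sided 5%. Normal approximation with pooled null variance:
- mean proportion 0.464; null SE = √(2 × 0.464 × 0.536 / 35) = 0.119
- alternative SE = √((0.714 × 0.286 + 0.214 × 0.786) / 35) = 0.103
- power = Φ((0.50 − 1.96 × 0.119) / 0.103) = 99.5%

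This agrees with the stated figure of more than 95%. At the Bonferroni level of 0.025 it is 98.8%.

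*Non-inferiority.* No SD is stated, so it is solved from the margin of 8, one-sided 5%, about 85% power, a true difference of 0 and 35 per arm:
- 35 = 2 × (SD × (1.645 + 1.036) / 8)², so SD = 8 × √17.5 / 2.681 = 12.5
- SE of a difference in means = 12.48 × √(2/35) = 2.98

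**Illustrating dilution**

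Assume a share f of patients in every arm in whom background training removes the between-arm difference completely. The documents give no value for f. The cited contrast becomes 8 × (1 − f). Suppose exergames truly add nothing over sham, so that without dilution they fall 8 points short of the comparator. The chance of declaring non-inferiority is then Φ(8f / 2.98 − 1.645).

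| Assumed f | Contrast (points) | False non-inferiority | Responder power, 0.05 | Responder power, 0.025 |
|---|---|---|---|---|
| 0 | 8.0 | 5.0% | 99.5% | 98.8% |
| 10% | 7.2 | 8.4% | 97.8% | 95.6% |
| 20% | 6.4 | 13.4% | 93.5% | 88.6% |
| 30% | 5.6 | 20.0% | 85.2% | 77.1% |

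Responder power is computed with the sham rate raised towards the active rate, 0.214 + f × 0.50.

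**The case against.** **Additive effects cancel.** If background training simply adds the same gain in each arm, 1:1:1 randomisation balances it and the contrasts do not move. Extra heterogeneity could also raise the SD, which works against non-inferiority. Both points stand. The harm is possible, not certain, and the table shows an upper case for each f because it assumes complete dilution in every exposed patient.

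**Exposure may be rare.** The Protocol's introduction says that time and cost limit the use of computer-assisted cognitive programmes. This also stands, and no range for f can be supported from the documents.

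**Symptomatic treatments may include cognitive rehabilitation.** The exclusion wording does not say drugs only, although Concomitant medications uses the term alongside dosage and administration frequency. Even on the broad reading the criterion bars only starts within 3 months. A longer-running programme still passes, and the continuation sentence then applies to it.

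**Adaptive against sham is an internal check.** Marked dilution would weaken that contrast visibly. At 10% to 20% it would not: responder power at the 5% level stays at 93.5% or more, and 6.4 to 7.2 points cannot be told from 8 with an SE of about 3.

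**Stable background care is a legitimate choice.** It fits the statement under Ethical conduct that the study does not interfere with standard care. An entry criterion respects this, because it changes who is enrolled and not what care anyone receives.

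A reader might infer that carry-over from completed courses is an equal threat, since the cited 6-month retention is twice the 3-month window. The documents do not support that weight. The endpoint is change from baseline, so a retained gain is largely in the baseline score already; patients lifted to 38 or above are not eligible; and the Protocol calls the retention literature conflicting. Nor do they support a matching washout for earlier exergame training, because the same sentence reports no retention for exergames.

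**Conclusion.** The gap is real: ongoing cognitive rehabilitation is not an exclusion, and its continuation is encouraged if it began at least 3 months before enrolment. Concurrent training is the main route to harm; completed courses are secondary. Such training can dilute both sham contrasts and ease non-inferiority, but the documents do not show that it will.

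The size cannot be computed from the Protocol. The illustrative rise in false non-inferiority from 5% to about 8% to 13% rests on three assumptions: full dilution in 10% to 20% of patients, an SD of about 12.5 that is implied and not stated, and exergames with no true effect over sham. Superiority on responders is more robust, with power of 95.6% and 88.6% at the 0.025 level under the same shares. The point merits a change because the correction is cheap and the margin has no slack to absorb attenuation.

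**What to change.** - In Eligibility criteria, add an exclusion for a cognitive rehabilitation or cognitive training programme that is ongoing at enrolment. Add one for a recently completed programme, with a window justified against the 6-month retention that the Protocol cites. An effect still present at 6 months does not by itself show that 6 months is long enough, so the choice needs a stated reason.
- Reconcile Forbidden treatments and interventions with that criterion, so that the continuation sentence does not extend to cognitive programmes in enrolled patients. With the entry criterion in place, no participant is asked to stop care.
- Make sure that prior and concurrent rehabilitation is recorded. Concomitant medications requires drug changes to be recorded, and the text has no equivalent for rehabilitation. The CRF is an appendix that is not shown and may already collect it.

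The cost is an eligibility amendment, possibly one CRF item, and slightly slower recruitment.

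### The non-inferiority claim does not depend on adaptive COGNI-TRAcK beating sham in this trial, so the stated 85% power is also the chance of making the claim when neither training works

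*Protocol*

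**What the plan says.** The Statistical Plan (Sample size estimation) gives non-inferiority its own null and alternative hypotheses, both about exergames against adaptive COGNI-TRAcK. Success is judged by the "lower limit of a one-sided 95% confidence interval (or equivalently a 90% two-sided confidence interval"), which "will be above the predefined non-inferiority margin of 8-point change in SDMT". The power figure is worked out under one condition, a true difference of zero: "If there is truly no difference between exergames and adaptive COGNI-TRAcK, then 35 patients per arm are required to ensure" this.

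The same section then opens a separate hypothesis: "For the superiority comparison, the null hypothesis is that the intervention with adaptive COGNI-TRAcK is not superior to sham COGNI-TRAcK". That test is sized on responder proportions, with more than 95% power at two-sided 5%.

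Under Pre-planned statistical significance level, the two active arms are each compared with sham, and "all analysis will be corrected with Bonferroni adjustment for multiple comparisons of two-sided tests", giving 0.025.

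The rationale for the study design lists superiority over sham and non-inferiority as hypotheses (i) and (ii). The primary objective in the synopsis joins them with *and*. No section orders the tests or says what happens to the non-inferiority claim if adaptive COGNI-TRAcK fails against sham.

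**The concern.** A non-inferiority result means something only if the comparator worked in the same trial. Exergames and adaptive COGNI-TRAcK can look alike because both improve SDMT or because neither does, and the stated rule gives the same answer in both cases.

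The comparator's effect over sham rests on one cited trial, whose responder counts were 10/14 and 3/14. If that effect is not reproduced here, the trial could still report exergames as not inferior to cognitive rehabilitation when neither had improved SDMT. The design already pays for a sham arm that could expose this, but the rule leaves it out.

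**Working it through.** **Inputs from the protocol.** Margin 8 SDMT points; 35 evaluable patients per arm; one-sided 5%; power about 85% at a true difference of 0; superiority level two-sided 0.025; adaptive-versus-sham effect about 8 points; responders 10/14 versus 3/14. The SD of SDMT change is not stated.

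**Step 1: the plan's own figure.** Power = Φ(margin / (SD × √(2/n)) − 1.645). Because the SD is missing, 35 per arm at 85% cannot be reproduced independently, but it can be solved backwards: SD = 8 × √(35/2) / (1.645 + 1.036) = 33.47 / 2.681 = 12.48. The noncentral t gives 12.36. Check: 12.48 × √(2/35) = 2.983; 8 / 2.983 = 2.682; Φ(2.682 − 1.645) = 85.0%.

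**Step 2: the same rule when nothing works.** The formula contains only the exergames-minus-adaptive difference, which is 0 if both trainings gain 8 points and 0 if both gain nothing. The 85% therefore carries over unchanged. This does not depend on the back-solved SD, because it is the protocol's own power statement. If the Bonferroni sentence also governs this test (one-sided 0.0125), the figure is Φ(2.682 − 2.241) = 67%.

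**Step 3: adding the gate.** I simulated 1,000,000 three-arm trials per scenario: 35 per arm, normal data, pooled variance, non-inferiority at one-sided 5%. The gate is adaptive superior to sham on mean SDMT change at two-sided 0.025.

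| Assumed SD | No effect: claim without gate | No effect: claim with gate | Both +8 over sham: claim with gate |
|---|---|---|---|
| 10 | 95% | 0.9% | 81% |
| 12.36 (implied) | 85% | 0.5% | 53.5% |
| 15 | 72% | 0.3% | 28% |

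At the implied SD with both trainings at +8, the gate alone passes in 67% of trials and non-inferiority in 85%. The joint figure is below the product of the two because a high adaptive mean helps the first test and hurts the second. With the gate at two-sided 0.05, the no-effect figure is 1.2% and the +8 figure is 62%.

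**Step 4: the responder test as gate.** With 35 per arm, 10/14 versus 3/14 gives 98.8% power at two-sided 0.025 (99.5% at 0.05). The joint probability is then at least 85% + 98.8% − 100% = 83.8%.

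**Step 5: is this only a matter of margin size?** No. With a 4-point margin at the implied SD, the ungated claim under no effect still occurs in 38% of trials.

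**The case against.** **The objectives are conjunctive.** The study hypothesis and the primary objective join non-inferiority and superiority with *and*. Read as a joint success criterion, this would already be a gate: all three comparisons would succeed in only about 0.2% of trials under no effect at 0.025. But the protocol never turns the *and* into a success rule, and the same template is reused for the secondary, additional and exploratory objectives. If joint success is meant, 85% is not its power either: at the implied SD with both trainings at +8, all three succeed in about 47% of trials. The Bonferroni split does not settle the matter, since it could simply be conservative.

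**The SAP may order the tests.** It may, and testing order is often left there. The point rests on what the protocol does fix: a stand-alone rule with its own power figure, which a gate would change.

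**85% is not an error rate.** A reader might infer an 85% false-positive rate. The documents do not support that: if all arms are equal, exergames really is within 8 points of adaptive COGNI-TRAcK. The sham comparison is also planned and would be seen beside the result. This stands, and it makes the issue one of interpretability.

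**The cost figures depend on the SD and the endpoint.** This also stands. The protocol reports p < 0.001 for an 8-point difference. With 14 per group and a simple t-test, that would need an SD of about 5.7 or less. Responder rates of 71% and 21% with an 8-point shift imply about 5.9 under normality. At SD 5.9 a gate on means costs almost nothing, but the ungated claim under no effect rises to about 100%, so the missing gate matters no less.

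**Conclusion.** The point holds as a gap in assay sensitivity. As written, the protocol would declare exergames non-inferior in about 85% of trials in which no arm has any effect, or about 67% if the Bonferroni level applies to this test. Both figures assume 35 evaluable patients per arm. A gate on mean SDMT change at two-sided 0.025 brings this to about 0.5% at the implied SD.

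Two stronger inferences are not supported. One is that the gated claim has a single power fixed by the protocol's own assumptions: the SD is unstated, and the protocol sizes adaptive versus sham on responders, not means. The other is that the Bonferroni rule should give way to a fixed sequence ending with exergames versus sham. At the implied SD, such a sequence at two-sided 0.05 would cut the chance of claiming exergames superior to sham from 67% to 2.5% if only exergames gains 8 points, and from 67% to 57% if both do. Only the non-inferiority claim needs the gate.

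**What to change.** Leave the two Bonferroni-adjusted superiority comparisons with sham as they are, and do not place exergames versus sham behind any other test. Add to the Statistical Plan that non-inferiority of exergames is claimed only if adaptive COGNI-TRAcK is superior to sham on a named SDMT endpoint (mean change to Week 8, or the responder definition) at two-sided 0.025. If it is not, the exergames-minus-adaptive difference and its confidence interval are reported descriptively, with no non-inferiority claim. State whether the 0.025 level also applies to the non-inferiority test.

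Replace the 85% with the probability of the gated claim, and give the assumed SD, gate endpoint and true effects. For both trainings at +8 and a gate on means, that is about 54% at SD 12.4, 81% at SD 10 and 28% at SD 15. With the responder gate it is close to 85%, provided the assumed 50% difference holds.

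The change needs no new patients or data. Its one downside is the lower stated power for the non-inferiority claim.
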